9 ASSESSMENT OF SAFETY

9.1 Adverse events

9.1.1 Definitions

9.1.1.1 Adverse event

An AE is any untoward medical occurrence in a patient or clinical investigation subject administered a pharmaceutical product that does not necessarily have a causal relationship with this treatment. An AE can therefore be any unfavorable and unintended sign (including an abnormal laboratory finding or echocardiogram), symptom, or disease temporally associated with the use of a medicinal (investigational) product, whether or not related to the medicinal (investigational) product.

In order to ensure complete safety data collection, all AEs occurring during the study (ie, after the signing of the ICF until the SFU Visit), including any pretreatment and posttreatment periods required by the protocol, must be reported in the eCRF even if no PSL was taken but specific study procedures were conducted. This includes all AEs not present prior to the initial visit and all AEs that recurred or worsened after the initial visit.

Signs or symptoms of the condition/disease for which the PSL is being studied (ie, seizures) should be recorded as AEs only if their nature changes considerably or their frequency or intensity increases in a clinically significant manner as compared with the clinical profile known to the Investigator from the subject's history, including their participation in parent studies.

9.1.1.2 Serious adverse event

Once it is determined that a subject experienced an AE, the seriousness of the AE must be determined. An SAE must meet 1 or more of the following criteria:

- Death
- Life-threatening
(Life-threatening does not include a reaction that might have caused death had it occurred in a more severe form.)
- Significant or persistent disability/incapacity
- Congenital anomaly/birth defect (including that occurring in a fetus)
- Important medical event that, based upon appropriate medical judgment, may jeopardize the subject and may require medical or surgical intervention to prevent 1 of the other outcomes listed in the definition of serious

(Important medical events may include, but are not limited to, potential Hy's Law [see [Section 9.1.1.3](#)]), allergic bronchospasm requiring intensive treatment in an emergency room or at home, blood dyscrasias that do not result in inpatient hospitalization, or the development of drug dependency or drug abuse)

- Initial inpatient hospitalization or prolongation of hospitalization

(A patient admitted to a hospital, even if he/she is released on the same day, meets the criteria for the initial inpatient hospitalization. An emergency room visit that results in admission to the hospital would also qualify for the initial inpatient hospitalization criteria. However, emergency room visits that do not result in admission to the hospital would not qualify for this criterion and, instead, should be evaluated for 1 of the other criteria in the definition of serious [eg, life-threatening adverse experience, important medical event].

Hospitalizations for reasons not associated with the occurrence of an AE [eg, preplanned surgery or elective surgery for a pre-existing condition that has not worsened or manifested in an unusual or uncharacteristic manner] do not qualify for reporting. For example, if a subject has a condition recorded on his/her medical history and later has a preplanned surgery for this condition, it is not appropriate to record the surgery or hospitalization as an SAE, since there is no AE upon which to assess the serious criteria. Please note that, if the pre-existing condition has worsened or manifested in an unusual or uncharacteristic manner, this would then qualify as an AE and, if necessary, the seriousness of the event would need to be determined.)

9.1.1.2.1 Anticipated serious adverse events

The following anticipated SAEs are anticipated to occur in the epilepsy population at some frequency that is independent of drug exposure.

This list does not change the Investigator’s obligation to report all SAEs (including Anticipated SAEs) as detailed in [Section 9.1.2](#).

Table 9–1: Anticipated SAEs for the epilepsy population

MedDRA System Organ Class	MedDRA Preferred Term
Congenital and hereditary disorders	Teratogenicity
General disorders and administration site conditions	Sudden unexplained death in epilepsy
Injury, poisoning, and procedural complication	Fall ^a , fracture ^a , injury ^a
Nervous system disorders	Cluster seizures, convulsion, incontinence ^a , memory impairment, status epilepticus
Pregnancy, puerperium, and perinatal disorders	Abortion spontaneous
Psychiatric disorders	Abnormal behavior, acute psychosis, anxiety, cognitive disorder, confusional state, psychotic behavior, sleep disorder and disturbances
Reproductive system and breast disorders	Impotence, menstrual disorder

MedDRA=Medical Dictionary for Regulatory Activities, Version 19.1; SAE=serious adverse event; SOC=System Organ Class

^a Event are anticipated when occurring in the context of seizure, but not classified in MedDRA primary SOC.

9.1.1.3 Adverse events of special interest

An AE of special interest is any AE that a regulatory authority has mandated to be reported on an expedited basis, regardless of the seriousness, expectedness, or relatedness of the AE to the administration of a UCB product/compound.

Potential Hy's Law, defined as $\geq 3 \times \text{ULN}$ ALT or AST with coexisting $\geq 2 \times \text{ULN}$ total bilirubin in the absence of $\geq 2 \times \text{ULN}$ ALP, with no alternative explanation for the biochemical abnormality, must ALWAYS be reported to UCB as an AE of special interest (ie, without waiting for any additional etiologic investigations to have been concluded). Follow up information should then be reported if an alternative etiology is identified during investigation and monitoring of the subject.

9.1.2 Procedures for reporting and recording adverse events

The subject will be given the opportunity to report AEs spontaneously. A general prompt will also be given at each study visit to detect AEs. For example:

“Did you notice anything unusual about your health (since your last visit)?”

In addition, the Investigator should review any self-assessment procedures (eg, diary cards) employed in the study.

9.1.3 Description of adverse events

When recording an AE, the Investigator should use the overall diagnosis or syndrome using standard medical terminology, rather than recording individual symptoms or signs. The eCRF and source documents should be consistent. Any discrepancies between the subject's own words on his/her own records (eg, diary card) and the corresponding medical terminology should be clarified in the source documentation.

Details for completion of the Adverse Event eCRF (including judgment of relationship to PSL) are described in the eCRF Completion Guidelines.

9.1.4 Rule for repetition of an adverse event

An increase in the intensity of an AE should lead to the repetition of the AE being reported with:

- The outcome date of the first AE that is not related to the natural course of the disease being the same as the start date of the repeated AE, and the outcome of “worsening”
- The AE verbatim term being the same for the first and repeated AE, so that the repeated AE can be easily identified as the worsening of the first one

9.1.5 Additional procedures for reporting serious adverse events

If an SAE is reported, UCB must be informed within 24 hours of receipt of this information by the site (see contact information for SAE reporting listed in the SAE Reporting section at the front of the protocol). The Investigator must forward to UCB (or its representative) a duly completed “Investigator SAE Report Form for Development Drug” (SAE report form) provided by UCB, even if the data are incomplete, or if it is obvious that more data will be needed in order to draw any conclusions. Information recorded on this form will be entered into the global safety database.

An Investigator SAE report form will be provided to the Investigator. The Investigator SAE Report form must be completed in English.

It is important for the Investigator, when completing the SAE report form, to include the assessment as to a causal relationship between the SAE and the PSL administration. This insight from the Investigator is very important for UCB to consider in assessing the safety of the PSL and in determining whether the SAE requires reporting to the regulatory authorities in an expedited manner. Expedited reporting to regulatory authorities will be in line with local laws.

Additional information (eg, autopsy or laboratory reports) received by the Investigator must be provided within 24 hours. All documents in the local language must be accompanied by a translation in English, or the relevant information included in the same document must be summarized in the Investigator SAE report form.

The Investigator is specifically requested to collect and report to UCB (or its representative) any SAEs (even if the Investigator is certain that they are in no way associated with the PSL), up to 6 months from last PSL intake for each subject (ie, until the 6-month follow-up echocardiogram), and to also inform participating subjects of the need to inform the Investigator of any SAE within this period. Serious AEs that the Investigator thinks may be associated with the PSL must be reported to UCB regardless of the time between the event and the end of the study.

Upon receipt of the SAE report form, UCB will perform an assessment of expectedness of the reported SAE. The assessment of the expectedness of the SAE is based on the IB.

9.1.6 Follow up of adverse events

An AE should be followed until it has resolved, has a stable sequela, the Investigator determines that it is no longer clinically significant, or the subject is lost to follow up.

If an AE is ongoing at the end of the study for a subject, follow up should be provided until resolution/stable level of sequelae is achieved, or until the Investigator no longer deems that it is clinically significant, or until the subject is lost to follow up. If no follow up is provided, the Investigator must provide a justification. The follow up will usually be continued for 30 days after the subject has discontinued his/her PSL.

Information on SAEs obtained after final clinical database lock will be captured through the Patient Safety (PS) database without limitation of time.

9.1.7 Pregnancy

If an Investigator is notified that a subject has become pregnant after the first intake of any PSL, the Investigator must immediately notify UCB's PS department by providing the completed Pregnancy Report and Outcome form (for contact details see SAE reporting information at the beginning of this protocol). The subject should be withdrawn from the study as soon as pregnancy is known (by positive urine pregnancy test), and the following should be completed:

- The subject should return for an EDV.
- The subject should immediately stop the intake of the PSL or be tapered as instructed at the EDV.
- Safety Follow-up Visit should be scheduled 1 week after the subject has discontinued PSL.

The Investigator must inform the subject of information currently known about potential risks and about available treatment alternatives.

The pregnancy will be documented on the Pregnancy Report and Outcome form provided to the Investigator. The progression of the pregnancy and the eventual birth (if applicable) must be followed up using the Pregnancy Report and Outcome form in which the Investigator has to report on the health of the mother and of the child. Every reasonable attempt should be made to follow the health of the child for 30 days after birth for any significant medical issues. In certain circumstances, UCB may request that follow up is continued for a period longer than 30 days. If the subject is lost to follow up and/or refuses to give information, written documentation of attempts to contact the subject needs to be provided by the Investigator and filed at the site. UCB's PS department is the primary contact for any questions related to the data collection for the pregnancy, eventual birth, and follow up.

In cases where the partner of a male subject enrolled in a clinical study becomes pregnant, the Investigator or designee is asked to contact the subject to request consent of the partner via the Partner Pregnancy Consent form that has been approved by the responsible IRB/IEC and should be available in the Investigator site file. In case of questions about the consent process, the Investigator may contact the UCB/contract research organization (CRO) contract monitor for the study. The Investigator will complete the Pregnancy Report and Outcome form and send it to UCB's PS department (for contact details see SAE reporting information at the beginning of this protocol) only after the partner has agreed that additional information can be captured and has provided the signed Partner Pregnancy Consent form. UCB's PS department is also the primary contact for any questions related to the data collection for the partner pregnancy, eventual birth, and follow up.

A pregnancy becomes a SAE in the following circumstances: miscarriage, abortion (elective or spontaneous), unintended pregnancy after hormonal contraceptive failure (if the hormonal contraceptive was correctly used), ectopic pregnancy, fetal demise, or any congenital anomaly/birth defect of the baby. Those SAEs must be additionally reported using the Investigator SAE Report form.

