5 STUDY DESIGN

5.1 Study description

This is an OLE study that will assess the safety, tolerability, and change in focal-onset seizure frequency associated with long-term oral PSL as an adjunctive therapy in adult subjects with drug-resistant epilepsy. This study will enroll consenting subjects, or subjects whose legal representatives have given consent, and who have completed a PSL parent study (eg, EP0091 or subsequent PSL studies).

At the Entry Visit (same day as the end of Conversion Period Visit in the parent study), subjects will sign a written Informed Consent form (ICF) prior to the conduct of any study-related procedure or pre-treatment assessments, and the subject's eligibility will be determined on the basis of the inclusion/exclusion criteria by the Investigator. Eligible subjects must be educated to record all types of seizures that occur in their seizure diary and to complete their diary entries after each seizure or at least once a day. A caregiver is allowed to help the subject with the completion of the subject diary.

Evaluation Period

After the Entry Visit (Visit 1), subjects will return to the clinic for visits as follows:

- Every 2 weeks during Month 1
- Every month during Month 2 and Month 3
- Every 3 months after Month 3 to the end of Year 2

Dose adjustment of PSL and/or concomitant AEDs and/or settings to neurostimulation devices is allowed at any time during the study, if seizure control is insufficient, or in case of safety or tolerability issue. Concomitant AED(s) may be tapered and discontinued to achieve PSL monotherapy, if clinically appropriate in which case the UCB Physician or delegate must be contacted to discuss with the Investigator. New concomitant AEDs, as allowed per protocol (see [Section 7.8.1](#)), may be introduced to optimize seizure control. Subjects who are not able to tolerate or who do not benefit from the PSL treatment may be tapered off PSL and withdrawn from the study.

Taper Period

Subjects who complete the study or who discontinue early will return for an End-of-Study Visit or EDV, respectively, and will be progressively tapered off over 4 weeks and return to the site 1 week after the last PSL intake for an end of Taper Visit. If a subject transfers into either a Managed Access Program or another PSL study, or takes commercially available PSL, the Taper Period may be skipped and the subject may continue treatment without tapering.

Safety Follow-up Period

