Safety follow up will consist of 1 required visit (SFU Visit) 30 days after the last PSL intake. A follow-up echocardiograms will be required at approximately 1 month and 6 months after the last PSL intake.

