 12. For subject developing psychiatric/mood/behavioral signs or disturbances (see examples in list below) that are clinically concerning or that worsen over time, the PSL dose should be gradually reduced and, if symptoms persist, withdrawal from the study should be considered. The subject should be referred to a mental health professional, and continuation of PSL should only be allowed with the approval and under close oversight of the mental health specialist, and upon confirmation of the positive benefit/risk by the Investigator.
 - Auditory or visual hallucinations
 - Delusions/paranoia/grandeur
 - Disorganized thought process
 - Agitation/aggression/apathy
 - Dysphoria/depression/mood lability/euphoria
 - Disinhibition
 - Cognitive changes/memory impairment/delirium
 - Aberrant motor behavior
 13. Subject is suspected of having a serious multiorgan hypersensitivity reaction. Serious suspected multiorgan hypersensitivity cases may be identified and reported to the Sponsor by the Investigator using the following algorithm:
 - An AE or laboratory value (as defined below) suggestive of internal organ involvement including but not limited to hepatitis, nephritis, pneumonitis, carditis, colitis, encephalitis, pancreatitis, myositis, arthritis, or hematologic system involvement combined with at least one of the following: fever, rash, lymphadenopathy, or eosinophilia.
 - Treatment-emergent abnormal laboratory value criteria suggestive of internal organ involvement or eosinophilia:
 - Eosinophils percentage $\geq 10\%$
 - Eosinophils absolute $\geq 0.5\text{G/L}$
 - Neutrophils absolute $< 1.5\text{G/L}$
 - Platelets absolute $\leq 100\text{G/L}$
 14. There is confirmation of a pregnancy during the study, as evidenced by a positive pregnancy test.

Investigators should attempt to obtain information on subjects in the case of withdrawal or discontinuation. For subjects considered as lost to follow up, the Investigator should make an effort (at least 1 phone call and 1 written message to the subject), and document his/her effort

(date and summary of the phone call and copy of the written message in the source documents), to complete the final evaluation. All results of these evaluations and observations, together with a narrative description of the reason(s) for removing the subject, must be recorded in the source documents. The eCRF must document the primary reason for withdrawal or discontinuation.

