8.3 Safety Follow-up

8.3.1 Safety Follow-up Visit (30 days after the last PSL intake) \pm 1 week

The following procedures will be performed for subjects discontinuing the study or completing it without continuation of PSL treatment:

- Obtain C-SSRS data since the last visit
- Obtain CIWA-B data
- Measure vital signs (pulse rate, systolic BP, diastolic BP, and respiratory rate), in supine position after 5 minutes of rest
- Measure body weight
- Perform brief physical examination (refer to [Section 9.3.4](#) for details)
- Perform brief neurological examination (refer to [Section 9.3.5](#) for details)
- Perform Psychiatric and Mental Status assessment
- Obtain 12-lead ECG
- Obtain echocardiogram
- Seizure evaluation (count and type) from subject's daily record card
- Record concomitant medication and procedures
- Record AEs
- Record health-related outcomes and HRU (refer to [Section 10.5](#) for details) with the exception of socio-professional status
- Call IRT
- End of diary recording
- Study termination

An echocardiogram will be performed 6 months after last PSL intake for all subjects.

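### Protocol 9.1.7 puts the Safety Follow-up Visit 1 week after stopping PSL for pregnancy withdrawals; everywhere else it is 30 days after the last intake

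*Protocol*

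**What the plan says.** Protocol 9.1.7 lists what must happen once a pregnancy is known. The subject is withdrawn, attends an Early Discontinuation Visit, and either stops PSL at once or tapers. The last item reads: "Safety Follow-up Visit should be scheduled 1 week after the subject has discontinued PSL".

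The general rule is different and appears in several places:

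- Protocol 5.1: "Safety follow up will consist of 1 required visit (SFU Visit) 30 days after the last PSL intake".
- Protocol 8.3.1 has the heading "Safety Follow-up Visit (30 days after the last PSL intake"), followed by a window of ±1 week. Its scope is given as: "The following procedures will be performed for subjects discontinuing the study or completing it without continuation of PSL treatment".
- The Safety Follow-up (SFU) column of Table 5-1 also gives 30 days after the last intake.

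Pregnant subjects are inside that scope, because withdrawal criterion 14 in Protocol 6.3 is: "There is confirmation of a pregnancy during the study, as evidenced by a positive pregnancy test".

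Two other provisions matter. Protocol 9.1.1.1 defines the adverse event collection period as "after the signing of the ICF until the SFU Visit". Protocol 5.1 already has a visit one week after the last intake, but it is a different one: subjects "return to the site 1 week after the last PSL intake for an end of Taper Visit".

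**The concern.** One named visit has two dates for the same subjects. Section 9.1.7 neither presents its timing as an exception nor says whether the 30-day visit still takes place. Because 5.1 requires only one SFU Visit, a site could reasonably take 9.1.7 as replacing it.

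The SFU Visit closes several things at once. Under 9.1.1.1 it ends collection of new adverse events. Under 8.3.1 it carries the CIWA-B withdrawal scale, the end of diary recording and study termination. Moving it to Day 7 moves all of these.

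The subjects affected include those who stop PSL abruptly, which 9.1.7 allows. PSL binds at the benzodiazepine receptor site and the protocol monitors for withdrawal, so early closure is least desirable in this group. The CIWA-B safety variable in Protocol 4.1.2 also runs to the end of an SFU period defined as 30 days after the last intake, and a Day 7 visit does not supply that measurement.

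The conflict also leaves deviation review (Protocol 12.5) without a clear standard. A single visit at Day 7 complies with 9.1.7 and breaches 8.3.1; a single visit at Day 30 does the reverse.

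**Working it through.** The plan has no figure of its own to reproduce. The check is a comparison of text plus day counts, with Day 0 as the last PSL intake.

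**Inputs**

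| Input | Value | Source |
|---|---|---|
| SFU Visit, pregnancy withdrawal | Day 7 | Protocol 9.1.7 |
| SFU Visit, discontinuing subjects | Day 30 | Protocol 5.1, 8.3.1, Table 5-1 |
| Visit window | ±7 days | Protocol 8.3.1 heading only |
| End of new adverse event collection | SFU Visit | Protocol 9.1.1.1 |
| End of Taper Visit | Day 7 | Protocol 5.1 |

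**Step 1: can the window reconcile the two dates?**
Permitted range under 8.3.1 = 30 − 7 to 30 + 7 = Day 23 to Day 37.
Gap from Day 7 to the earliest permitted day = 23 − 7 = 16 days.
Gap from Day 7 to the latest permitted day = 37 − 7 = 30 days.
Day 7 is outside the window, so no allowed visit satisfies both rules.

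**Step 2: does another reading of the starting point help?**
If discontinuation in 9.1.7 meant the start of the taper, the 1-week visit would fall during the taper, before the last intake. That widens the gap.

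**Step 3: how much collection could be lost per affected subject?**

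- Both visits held: 0 days lost.
- Day 7 replaces the nominal Day 30 visit: 30 − 7 = 23 days; 23/30 = 77%.
- Day 7 replaces the earliest permitted visit (Day 23): 23 − 7 = 16 days.

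**Step 4: which rule is the outlier?**
Protocol 5.1, 5.1.1, 8.3.1, Table 5-1 and 4.1.2 all attach 30 days to the SFU Visit or period, and so does SAP 9.2. Only 9.1.7 says 1 week. For a tapered subject it also puts the SFU Visit on the same nominal day as the End of Taper Visit, merging two visits that Table 5-1 keeps apart.

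**The case against.** The best defence is that 9.1.7 is a deliberate rule for one situation. An early check after abrupt cessation is clinically sensible, and specific text is commonly taken to govern over general text. That is possible. But the section uses the defined name of the visit, does not call it additional, and does not say that the 30-day visit is waived or retained. Even on this reading the text needs correcting.

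A second argument is that the 77% loss is a worst case. SAP 9.2 describes adverse event recording as running to the end of an SFU period 30 days after the last intake. Protocol 9.1.6 says follow-up of adverse events usually continues for 30 days after stopping PSL. Protocol 5.1 calls for an echocardiogram at about 1 month, which would bring the subject back. These points stand as limits on the likely effect. They do not remove the conflict: the SAP does not instruct sites, 9.1.1.1 ties the end of collection to the visit, and 9.3.3, 8.3.1 and Table 5-1 footnote k make the 1-month echocardiogram part of the SFU Visit itself. The SAP's 30 days also supports the view that 9.1.7 is the error.

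Third, the practical reach is small. SAP 3.9 records early termination of the study, so a correction now may affect few or no subjects. That is fair and bears on priority.

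**Conclusion.** The contradiction is real and lies in the operative text. Section 9.1.7 is wrong as written for a visit that the rest of the protocol fixes at 30 days.

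Per affected subject, the loss of new non-serious adverse event collection ranges from 0 days, if both visits are held, to 23 of 30 days, if the Day 7 visit replaces the nominal 30-day one. The upper figure assumes that the site drops the later visit and closes recording at Day 7. The documents give no expected number of pregnancies; few are likely because contraception is mandatory (Protocol 6.1).

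Severity is low. SAEs are collected "up to 6 months from last PSL intake for each subject" (Protocol 9.1.5), and ongoing adverse events and the pregnancy itself are followed (9.1.6, 9.1.7). The SAP's Taper/Safety Follow-up period ends at final contact (table in SAP 3.2.3), so no derivation fails. The point concerns completeness of safety follow-up and does not affect any efficacy result.

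**What to change.** Replace the last item of the list in Protocol 9.1.7 with: *The Safety Follow-up Visit should be scheduled 30 days (±1 week) after the last PSL intake, as in Section 8.3.1.*

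If a 1-week check is wanted, keep it under a different name. For tapered subjects it is the End of Taper Visit that 5.1 already provides. For subjects who stop at once, make it an additional unscheduled visit under 8.4. In both cases, state that it does not end adverse event collection, diary recording or study participation.

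The cost is a one-sentence protocol correction, with whatever sponsor, ethics and regulatory approval Protocol 13.3 and 13.5 require. It adds no procedure beyond those in 8.3.1, apart from the optional 1-week visit, and needs no SAP change. Given the early termination, it could be made with any other remaining amendment, and the corrected wording should be carried into later PSL protocols that reuse this section.
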